Fluoroquinolones are contraindicated with patients with known history of myasthenia gravis, because they have neuromuscular blocking activity and may exacerbate muscle weakness.

The overdose may lead to loss of appetite, diarrhea, metallic taste, headache, dizziness, insomnia or drowsiness.

The following is a list of possible side effects that may occur, rarely, from the use of Ciprofloxacin[®] tablets:

- Allergic reactions such as rash, itching, and swelling of the mouth, face, lips, or tongue
- Nausea, headache, anorexia, diarrhea, unpleasant metallic taste, stomach cramps pain, vomiting, fainting, and fever.
- Reversible neutropenia (leukopenia), and blood dyscrasias.
- Dysuria, darkening of urine, cystitis, bloody stools, abdominal and vaginal yeast infection.
- Tendon inflammation and damage.
- Irregular heartbeat and loss of consciousness.
- Mood or mental changes such as anxiety, confusion, depression, and sleeplessness.
- Convulsive seizures and peripheral neuropathy tremors.
- Jaundice.

8.5.1 Storage and Drug Accountability:

Study drugs are to be stored at room temperature up to 30 degrees C (86 degrees F). Keep them in the original containers. Store away from heat, moisture, and light. Do not store in the bathroom. Keep them out of the reach of children and away from pets.

All empty, partially used, and unused blisters will be retained by the Investigator (at room temperature) until they are returned to the pharmacist and to be checked by monitor.

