The simultaneous administration of drugs that induce microsomal liver enzymes, such as Phenytoin or Phenobarbital, may accelerate the elimination of metronidazole while the simultaneous administration of drugs that decrease microsomal liver enzymes activity, such as ceftrimide, may prolong the half-life and decrease plasma clearance of metronidazole.

Ciprofloxacin may increase the effects of caffeine.

Serious and fatal reactions have occurred when Ciprofloxacin was taken in combination with theophylline. These reactions have included cardiac arrest, seizures, status epilepticus, and respiratory failure.

Tendon disorders (tendinitis) have been rarely encountered in some cases related to concomitant use of quinolone with corticosteroids.

9 Research Question & Study Objectives

9.1 Primary Objective:

9.1.1 Primary Safety:

To compare safety of oral Ciprodiazole[®] tablets (Ciprofolxacin/Metronidazole) versus currently used Ciprofloxacin Tablets & Metronidazole tablets in pelvi-abdominal infections, either non-operative or post-operative following IV antibiotics.

9.1.2 Primary Efficacy:

To compare efficacy of oral Ciprodiazole[®] tablets (Ciprofolxacin/Metronidazole) versus currently used Ciprofloxacin Tablets & Metronidazole tablets in pelvi-abdominal infections, either non-operative or post-operative following IV antibiotics

9.2 Secondary Objective:

9.2.1 Secondary Safety:

- Presence of any signs/symptoms of post-operative wound infection such as redness, fever or wound discharge.
- Presence of undesirable effects on total leukocyte count and liver enzymes (SGOT & SGPT)

9.2.2 Secondary Efficacy:

- To compare the complete resolution or improvement of Pelvi-abdominal infection between ciprodiazole[®] versus combined treatment, based on pelvi-abdominal ultrasound and others
- To compare the days for complete healing of post-operative wounds between ciprodiazole[®] versus combined treatment

10 Research Methods

10.1 Study Design:

This is a single center, open Label, controlled, interventional phase IV Study conducted in Menoufia University Hospital in Egypt to compare the safety and efficacy of oral Ciprodiazole[®] tablets (Ciprofloxacin/Metronidazole) versus currently used Ciprofloxacin Tablets & Metronidazole tablets in pelvi-abdominal infection and following IV antibiotics in post-operative period, for pelvi-abdominal surgeries or acute conditions

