- Presence of any signs/symptoms of post-operative wound infection such as redness, fever or wound discharge will be recorded (in case of post-operative subjects)
- Safety laboratory tests (including Total Leucocytic count, Liver enzymes (SGOT & SGPT), Total Bilirubin and S. Creatinine)
- The End of Study Form must be completed.

10.3 Variables:

10.3.1 Primary Endpoints:

1- *Primary Safety:*

Incidence of serious/non-serious adverse events

2- *Primary Efficacy:*

- Complete resolution for pelvi-abdominal infection based on pelvi-abdominal ultrasound and others and/or clinical response
- Complete healing of post-operative wounds

10.3.2 Secondary Endpoints:

1- *Secondary Safety:*

- Presence of any signs/symptoms of post-operative wound infection such as redness, fever or wound discharge.
- Change in Total leukocytes count and Liver enzymes (SGOT, SGPT), between baseline (visit 1) to End of study visit (Follow up 2 visit)

-

2- *Secondary Efficacy:*

- Describe complete resolution, improvement, failure or relapse of pelvi- abdominal infection based on pelvi-abdominal ultrasound and others and or clinical response.
- Days for complete healing of post-operative wounds after 8 days of treatment (Follow-up 1 V) & 15 days of treatment (End of study visit) between the 2 groups

10.4 Data Sources:

All visits assessments will be kept in the source files for each patient and in CRF, which will be verified by the CRA responsible.

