10.7.5 Other criteria

- To describe presence of any signs/symptoms of post-operative wound infection such as redness, fever or wound discharge.
- To describe presence of undesirable effects on total leukocyte count and liver enzymes (SGOT & SGPT) between baseline (visit 1) to End of study visit (Follow up 2 V)
- To compare the complete resolution, improvement, failure or relapse of Pelvi- abdominal infection between ciprodiazole® versus combined treatment, based on pelvi-abdominal ultrasound and others
- To compare the number of days for complete healing of post-operative wounds between ciprodiazole® versus combined treatment

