Frequency distribution (number & percent) of presence of any signs/symptoms of post-operative wound infection such as redness, fever or wound discharge. Chi² test will be used to determine *p*-value and significance between the 2 groups.

B. Change in Total leukocytes count between baseline (visit 1) to End of study visit

Descriptive analysis (mean, Standard Deviation, Median, Interquartile Range, Minimum and Maximum) of total leucocyte will be from baseline (visit 1) to End of study visit. Percent change will be calculated between baseline to End of study. Paired t-test will be used to determine *p*-value and significance between baseline and at the end of the study. Unpaired t-test will be used to determine the *p*-value and significance between Changes in total leucocyte between 2 groups.

C. Change in Liver enzymes (SGOT) between baseline (visit 1) to End of study visit

Descriptive analysis (mean, Standard Deviation, Median, Interquartile Range, Minimum and Maximum) of Liver enzymes (SGOT) will be from baseline (visit 1) to End of study visit. Percent change will be calculated between baseline to End of study. Paired t-test will be used to determine *p*-value and significance between baseline and at the end of the study. Unpaired t-test will be used to determine the *p*-value and significance between Changes in Liver enzymes (SGOT) between 2 groups.

D. Change in Liver enzymes (SGPT) between baseline (visit 1) to End of study visit

Descriptive analysis (mean, Standard Deviation, Median, Interquartile Range, Minimum and Maximum) of Liver enzymes (SGPT) will be from baseline (visit 1) to End of study visit. Percent change will be calculated between baseline to End of study. Paired t-test will be used to determine *p*-value and significance between baseline and at the end of the study. Unpaired t-test will be used to determine the *p*-value and significance between Changes in Liver enzymes (SGPT) between 2 groups.

10.7.9 Secondary Efficacy analysis:

A. Complete resolution, improvement, failure or relapse of Pelvi- abdominal infection

- Frequency distribution (number & percent) of complete resolution, improvement, failure or relapse for Pelvi- abdominal infection. Chi² test will be used to determine *p*-value and significance between the 2 groups.
- Frequency distribution (number & percent) of improvement for Pelvi- abdominal infection. Chi² test will be used to determine *p*-value and significance between the 2 groups.

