9.5 Secondary End Point

9.5.1 Secondary Safety:

Table 11 *Number and percent of signs/symptoms of post-operative wound infection among treatment groups*

	Group A (N=156)	Group B (N=156)	p-value
No of signs/symptoms of post-operative wound infection, N (%)			
Redness, N (%)			
Fever, N (%)			
Wound discharge, N (%)			

Table 12 *Percent Change in mean Total leukocytes among treatment groups*

	Group A (N=156)	Group B (N=156)	p-value
Visit 1, mean ± SD			
End of study visit, mean ± SD			
% Change			
p-value between V1 & End of study visit			
p-value between 2 groups			

Table 13 *Percent Change in mean SGOT among treatment groups*

	Group A (N=156)	Group B (N=156)	p-value
Visit 1, mean ± SD			
End of study visit, mean ± SD			
% Change			
p-value between V1 & End of study visit			
p-value between 2 groups			

Table 14 *Percent Change in mean SGPT among treatment groups*

	Group A (N=156)	Group B (N=156)	p-value
Visit 1, mean ± SD			
End of study visit, mean ± SD			
% Change			
p-value between V1 & End of study visit			
p-value between 2 groups			

9.5.2 Secondary Efficacy:

Table 15 Number and percent of complete resolution, improvement, failure or relapse for Pelvi- abdominal infection among treatment groups

	Group A (N=156)	Group B (N=156)	p-value
Complete resolution, N (%)			
Improvement, N (%)			
Failure or relapse, N (%)			

Table 16 *Percent Change in mean days for complete healing of post-operative wounds after 8 days of treatment (Follow up 1 visit) among treatment groups*

	Group A (N=156)	Group B (N=156)	p-value
Visit 1, mean ± SD			
Follow up 1 visit, mean ± SD			
% Change			
p-value between V1 & Follow up 1 visit			
p-value between 2 groups			

Table 17 *Percent Change in mean days for complete healing of post-operative wounds after 15 days of treatment (Follow up 2 visit or End of study visit) among treatment groups*

	Group A (N=156)	Group B (N=156)	p-value
Visit 1, mean ± SD			
Follow up 2 visit, mean ± SD			
% Change			
p-value between V1 & Follow up 2 visit			
p-value between 2 groups			

10 Reference:

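### Post-baseline bilirubin and creatinine have no planned analysis, and leukocytes, SGOT and SGPT are compared only as groups, so abnormal values appear as cases only if the investigator records them as adverse events

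*Protocol*

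**What the plan says.** **Collected.** Protocol 10.2.4 lists for Follow-up 2 "Safety laboratory tests (including Total Leucocytic count, Liver enzymes (SGOT & SGPT), Total Bilirubin and S. Creatinine". The same four items, plus fasting blood sugar, are taken at screening, and the visit schedule in 12.3 agrees. Under 12.3.2, a patient with complete resolution at Day 8 has the end-of-study laboratory tests then. Each patient should therefore have one baseline value and one later value.

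**Objective and endpoint.** Protocol 9.2.1 states the secondary safety objective as "Presence of undesirable effects on total leukocyte count and liver enzymes (SGOT & SGPT"), and 10.7.5 repeats it as "To describe presence of undesirable effects on total leukocyte count and liver enzymes (SGOT & SGPT"). The endpoint in 10.3.2 is "Change in Total leukocytes count and Liver enzymes (SGOT, SGPT), between baseline (visit 1) to End of study visit (Follow up 2 visit").

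**Analysis.** Protocol 10.7.8 B specifies "Descriptive analysis (mean, Standard Deviation, Median, Interquartile Range, Minimum and Maximum) of total leucocyte will be from baseline (visit 1) to End of study visit", then a percent change, a paired t-test within group, and "Unpaired t-test will be used to determine the *p*-value and significance between Changes in total leucocyte between 2 groups". Parts C and D treat SGOT and SGPT in the same way, and SAP 8.8 B to D matches. SAP Table 12 is titled "Percent Change in mean Total leukocytes among treatment groups". It and Tables 13 and 14 have rows only for mean ± SD at two visits, percent change and p-values.

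**Listed risks.** Protocol 8.5 names "Reversible neutropenia (leukopenia), and blood dyscrasias" and, in the same list, jaundice. Sections 8.2 and 8.6 put abnormal liver tests among the most frequent ciprofloxacin effects.

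**The concern.** Whether an undesirable effect is present is a question about individual patients. A mean, a percent change and a t-test answer a different one: whether the average moved. A few marked abnormalities among 156 patients barely move an average.

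Two of the five tests are not followed up at all. Bilirubin bears directly on a listed risk, and creatinine is the test by which renal impairment is excluded at entry, yet neither has an analysis after baseline.

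For leukocytes the mean is also hard to interpret. Patients enter with infection or soon after surgery, so counts can be expected to fall as they recover. A falling mean may be cure, leukopenia or both, and the planned test cannot separate them.

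At stake is whether a safety comparison of the two arms can show how many patients in each had an abnormal liver, renal or leukocyte result.

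**Working it through.** **1. Tests collected against tests analysed.**

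| Test | Visit 1 and End of Study | Post-baseline analysis (Protocol 10.7.8, SAP 8.8) | SAP table | Limit or patient count |
|---|---|---|---|---|
| Leukocytes | Yes | Group summary, t-tests | 12 | None |
| SGOT | Yes | Group summary, t-tests | 13 | None |
| SGPT | Yes | Group summary, t-tests | 14 | None |
| Total bilirubin | Yes | None | None | None |
| Creatinine | Yes | None | None | None |

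Protocol 14.2 summarises laboratory assessments among the baseline characteristics and refers the analysis to section 10.7. It does not fill the two empty rows.

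**2. The adverse-event route.** Protocol 8.1 makes an out-of-range value an adverse event if the investigator sees a reasonable possibility that the drug caused it. Protocol 13.1 defines a laboratory adverse event differently: the value must suggest disease or organ toxicity and be severe enough to need active management (dose change, stopping the drug, closer follow-up or further investigation). One test is causality, the other is action taken, and neither has a numeric limit. The later sample is taken at End of Study, when the first two of those four actions have little scope left. The investigator knows the arm. Identical values could be recorded as an event in one patient and not in another.

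**3. How far a few cases move the mean.** The documents give no laboratory figure to reproduce. From them I take only 156 per arm (Protocol 10.5.1). The rest is assumed: 3 patients in one arm rise by 270 U/L in SGPT, none in the other arm; everyone else has mean change 0 and SD 15 U/L; all 156 per arm have both samples.

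- Proportion affected: q = 3/156 = 0.0192.
- Shift in mean: q × 270 = 5.19 U/L.
- Variance of change, affected arm: 15² + q(1 − q) × 270² = 225 + 1,375 = 1,600, so SD about 40.
- Standard error of the difference: √((1,600 + 225)/156) = 3.42.
- t = 5.19/3.42 = 1.52, p = 0.13.
- Repeating with SD 10: t = 1.63, p = 0.10. With SD 20: t = 1.39, p = 0.17.

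A simulation (4,000 runs, 156 per arm, SD of change 8 to 20 U/L, three cases rising by 100 or 200 U/L) agrees: the mean moves by 1.9 to 3.8 U/L, and the unpaired t-test is significant in about 10% to 19% of runs. With five cases the range is about 18% to 74%.

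**4. What a count would show.** The example would read 3/156 against 0/156, Fisher p = 0.25. Five against none gives p = 0.06. The count does not produce significance either. It states how many patients were affected.

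**5. Limits already in the documents.** The exclusion criteria (Protocol 10.2.2) remove patients with SGOT or SGPT above 2 times normal and creatinine above 1.5 mg/dL. In a correctly enrolled patient, a value beyond either limit at End of Study is new since entry.

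**The case against.** The strongest reply is that cases do have a way into the results. Protocol 8.1 requires investigators to evaluate all laboratory abnormalities, and 13.1 defines laboratory adverse events. Adverse events are analysed by type and severity as primary safety (Protocol 10.7.6, SAP 8.6 and Table 8) and tabulated by preferred term (Protocol 14.2). Clinical jaundice would be an ordinary adverse event. This stands. A reader might infer that cases of the listed risks cannot reach the results; the documents do not support that. What can be lost is the abnormal value that the investigator neither attributes to the drug nor acts on.

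A reader might also infer that mean percent change is the only summary. The analysis text plans median, interquartile range, minimum and maximum as well, so in the example the maximum would expose one extreme SGPT value, and the affected arm's SD would be enlarged. The SAP table shells drop the median, interquartile range, minimum and maximum, and a maximum still does not say how many patients were affected or whether bilirubin rose in the same patient.

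Protocol 10.7.3 promises a descriptive analysis of the collected data. It names no test, so it cannot be relied on for bilirubin or creatinine.

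It is tempting to size the leukocyte problem from the cited 74% and 63% resolution rates. Those compare ciprofloxacin plus metronidazole with a different regimen; here both arms receive ciprofloxacin and metronidazole. The documents give no expected cure difference between the arms and no baseline leukocyte level, so this part is qualitative.

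Lastly, the visit schedule pairs SGOT with ALT and SGPT with AST, which is crossed. A reader might infer misfiled results, but the endpoints, analyses and tables use SGOT and SGPT throughout, and nothing shows that results arrive under the other names. It is a clerical slip.

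**Conclusion.** The point holds as a gap in the analysis plan that should be closed. Two of five collected tests have no planned post-baseline analysis, and none of the five has a limit or patient count to answer an objective worded as the presence of effects. Abnormal values become cases only through open-label investigator judgement under two criteria that do not agree. For leukocytes, mean change cannot separate recovery from leukopenia; this rests on the expectation that counts fall as infection or the post-operative response settles.

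The size is illustrative: three marked SGPT rises in one arm move the mean by 5.2 U/L, with p between 0.10 and 0.17. That depends on the assumed rise, the assumed SD of 10 to 20 U/L and complete samples. It does not show that such cases would be invisible, only that the planned comparison would not count them.

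**What to change.** In Protocol 10.7.8, SAP 8.8 and SAP Tables 12 to 14:

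1. Add total bilirubin and creatinine with the same baseline-to-End-of-Study summary as the other three tests, with matching tables.
2. For all five tests, report n (%) per arm outside a pre-set limit at End of Study, with baseline-to-end shift tables. Use SGOT and SGPT above 2 times normal and creatinine above 1.5 mg/dL from the exclusion criteria, and the laboratory's normal range for bilirubin and leukocytes. These are limits for analysis only, not rules for managing patients.
3. Make the count of patients below the lower leukocyte limit the leukocyte safety result, and state that mean change also reflects response to treatment.
4. Reconcile the laboratory adverse-event definitions in Protocol 8.1 and 13.1.

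Correct the enzyme labels in the visit schedule at the same time.

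The cost is a few tables from data already collected, with no new samples. Protocol 10.7.2 and SAP 8.2 allow documented differences in the final SAP before database lock; item 4 and the label correction are changes to protocol text. Counts this small will rarely be significant, and reusing entry limits is a convention that should be stated as such. The gain is that affected patients can be seen and compared by arm.

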10.7.10 Interim analysis

Optional

10.7 Quality Control

10.8.1 Quality Assurance

To ensure uniformity of study procedures across centers, the protocol, case report form, and safety reporting procedures will be reviewed with the investigators and his/her personnel responsible for the conduct of the study. Adherence to the protocol and verification of source data will be achieved through monitoring visits to the center. During the course of study monitoring, the entire study documentation will be checked for completeness and plausibility by the responsible CRA. Once the CRF is completed and signed, the CRA takes the data management copy and the data is entered into the database for analysis. CRFs will be kept in secure locked place or lockers.

10.8 Limitation of the research methods

Any issues relating to confounding, bias, generalizability, and random error are considered as a limitation to the study results. This study is randomized, open label, controlled study, which avoids bias from the physicians, patients or biostatistician. Also, the study results are taken upon source document verification with the CRF in order to ensure the quality and non-bias of the data.

11 Protection of Human Subjects

This study will be conducted according to Good Clinical Practice (ICH-GCP) and in accordance with the Declaration of Helsinki as adopted by the 18th World Medical Assembly 1964 and subsequent amendments: Tokyo (1975), Venice (1983), Hong Kong (1989), Somerset West, Republic of South Africa (1996) and Edinburgh (2000).

This study will be conducted in compliance to Good Clinical Practice (ICH-GCP) and in accordance with the Declaration of Helsinki, with a qualified principle investigator.

Before the start of the study, subjects who appear suitable for inclusion in the study will be informed, as outlined in the protocol, about the objective, nature, scope, and potential benefits and risks of the study and any discomfort it may entail. The subject will be allowed sufficient time to reach a decision. The subject's consent will be documented on the form provided, which will be retained by the investigator; a copy of the informed consent declaration will be given to the subject to retain. Under the circumstances where signed informed consent is difficult to obtain from subjects due to illiteracy, witness should sign that the subject has been informed about all details of informed consent. The informed consent will be also signed and dated by the person who obtained the informed consent and signed/finger printed by the study participant, or his legal representative.

The subject will be assured that all personal data would be treated in strict confidence. In the event that information of relevance to the subject became available during the study, this will be communicated to the subject. The subject has the right to withdraw the informed consent at any time. No study-specific investigations would be performed and no study-

specific medication will be administered before informed consent is obtained .Case Report Forms will be provided for each subject's data to be recorded.

12 Study Procedures:

12.1 Informed consent:

- The investigator must provide the patient with relevant, comprehensive, verbal and written information regarding the objectives and procedures of the study as well as the possible risks involved, as per ICH-GCP guidelines.
- The patient should have enough time and opportunity to inquire about study details. All their questions should be answered in satisfying manner.
- The patient must be informed about their right to withdraw from the study at any time, without having to give a reason.
- Signed and dated informed consent must be obtained from all patients and in case of an illiterate patient, the patient will finger print with a witness who will sign and date, before undertaking any study related procedures, without any pressure or unduly influence from the treating doctor.

